8.2 Guide for assessment of overall efficacy for surgeries

The evaluation of overall efficacy of the treatment in surgeries based on the intraoperative and postoperative assessment is defined as described below:

Intraoperative assessment	Postoperative assessment			
	Excellent	Good	Moderate	None
Excellent	Excellent	Good	Good	Moderate
Good	Good	Good	Moderate	Moderate
Moderate	Good	Moderate	Moderate	None
None	Good	Moderate	None	None

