7.2.5.3 Overall Efficacy Assessment at the End of the Postoperative Period (by Investigator)

Overall efficacy using the ‘excellent,’ ‘good,’ moderate,’ and ‘none’ scale taking both the intra- and postoperative assessments into account will be assessed by the Investigator.

Table 5 Algorithm for the Overall Efficacy Assessment for Surgical Prophylaxis

Intraoperative assessment	Postoperative assessment			
	Excellent	Good	Moderate	None
Excellent	Excellent	Good	Good	Moderate
Good	Good	Good	Moderate	Moderate
Moderate	Good	Moderate	Moderate	None
None	Moderate	Moderate	None	None

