Efficacy assessment				S			H		
Overall efficacy assessment							I		
FVIII inhibitor								x	
Narrative of outcome							x		
Concomitant medications	throughout observation period								
Adverse event monitoring	throughout observation period								

POP, postoperative, VWF:Ag = von Willebrand factor antigen, VWF:Ac = VWF activity

() Optional

Samples to be taken immediately before (≤ 30 min) and 30 ± 15 min after IMP administration

[1] Time immediately after the last surgical suture

[2] For major surgery, mandatory for the first 3 postoperative doses

S, performed by surgeon; H, performed by hematologist; I performed by Investigator

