3.2 Deviations from the trial protocol with regard to statistical analyses

No deviations from the protocol are planned.

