5.9 Surgeries

Efficacy in surgical prophylaxis will be analyzed descriptively, presenting summary tables and listing on all aspects of surgical treatment and procedures as well as efficacy ratings.

The following surgery-related parameters will be presented:

- Number of minor and major surgeries

STATISTICAL ANALYSIS PLAN

Protocol No: WIL-27

Version Number: 5.0

Date of Issue: 2018-05-08

Page 22 of 27

- Location, severity (minor or major, for definitions see protocol), and type (planned or emergency) of surgery
- Expected and actual duration of surgical procedure
- Expected and actual blood loss
- Pre-, intra-, and/or postoperative IMP administration data (only listed)
- Pre-, intra-, and postoperative FVIII plasma levels (only listed)
- VWF:Ag and VWF:Ac (descriptive statistics including changes to pre-infusion)
- Presence of wound hematomas and whether or not they require surgical evacuation (only listed)
- Assessment of efficacy of surgical prophylaxis:
 1. at the end of surgery by the surgeon
 2. at end of the postoperative period by the hematologist
 3. Overall efficacy taking both the intra- and postoperative assessments into account assessed by the Investigator.
- Number of successively treated surgeries ('excellent' or 'good' overall efficacy rating)
- Concomitantly administered products (only listed)
- Narrative describing the outcome and efficacy of the intervention (only listed)
- Inhibitor testing (within 3–8 weeks after the end of the surgery, this visit may coincide with another study visit with scheduled inhibitor testing)

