8 APPENDICES

8.1 Formulas for derived variables

Variable	Description
Durations between two dates	Later date minus earlier date plus 1, expressed in days. (Remark: Duration will be 1, if both dates are the same.)
Annual bleeding rate	Number of bleedings under prophylaxis / time under prophylaxis (days)/365.25 (see prophylactic treatment phase)
AUC	Area under the curve from baseline to infinity $AUC = \sum \left(\frac{(C_n + C_{n+1})}{2} \cdot \Delta t \right) + \frac{C_{last}}{K}$ (C_{last} is the last available measurement)
AUC _{norm}	AUC normalized for the administered dose
AUMC	Area under the moment curve (from baseline to infinity) $AUMC = \sum \left(\frac{(t_n \cdot C_n + t_{n+1} \cdot C_{n+1})}{2} \cdot \Delta t \right) + \frac{C_{last}}{K^2} + \frac{t_{last} \cdot C_{last}}{K}$
CL	Clearance $CL = \frac{D}{AUC}$ where D is the actual dose administered (see remark above)
C_0	FVIII concentration before IMP administration
C_{max}	Maximal measured concentration after end of IMP infusion (peak concentration)
ED	Exposure day = each day the subject received IMP
Incremental recovery (IVR)	$IVR = \frac{(C_{max} - C_0) \cdot BW}{D}$

STATISTICAL ANALYSIS PLAN

Protocol No: WIL-27

Version Number: 5.0

Date of Issue: 2018-05-08

Page 26 of 27

	where BW stands for the body weight in kg and D is the dose according to the actual potency of the FVIII concentrate as described in above
MRT	Mean residence time $MRT = \frac{AUMC}{AUC}$
Prophylactic treatment phase	PK subgroup: (date of completion visit or date of last treatment with IMP in case completion visit not performed) – (date of first prophylactic treatment after the PK visit) Non-PK subgroup: (date of completion visit or date of last treatment with IMP in case completion visit not performed) – (date of first IMP infusion at Non-PK visit)
Success (for bleeding episodes and surgeries)	Excellent or good efficacy rating
T _{1/2}	In vivo half-life using linear regression on the terminal phase of the logarithm of the concentration; $T_{1/2} = \frac{\ln(2)}{K}$ (where K, the elimination rate constant, is determined as the slope of the regression line)
T _{max}	Time to reach maximum plasma concentration (Timing starts at end of infusion)
Vd	Volume of distribution $Vd = CL \cdot MRT$

STATISTICAL ANALYSIS PLAN Protocol No: WIL-27	
Version Number: 5.0 Date of Issue: 2018-05-08	Page 27 of 27

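### SAP 8.2 rates a surgery with intraoperative None and postoperative Excellent as Good, whereas Table 5 of protocol version 03 rates it Moderate; the two tables need to be reconciled

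*SAP*

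**What the plan says.** Protocol 7.2.5.3 has the Investigator give an overall efficacy rating for each surgery that takes the intraoperative and postoperative ratings into account. Its Table 5 supplies the algorithm, with intraoperative ratings in rows and postoperative ratings in columns. The columns run Excellent, Good, Moderate, None. The row for intraoperative None is "None Moderate Moderate None None" (row label first).

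SAP 8.2 introduces a table with the same layout as the definition of overall efficacy. Its row for intraoperative None is "None Good Moderate None None".

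Three other parts of the SAP bear on how the rating is used:

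- SAP 5.9 lists the overall assessment as "Overall efficacy taking both the intra- and postoperative assessments into account assessed by the Investigator", and the surgical flow chart in SAP 2.4 marks it with an I (legend: "S, performed by surgeon; H, performed by hematologist; I performed by Investigator").
- SAP 5.9 then plans to report "Number of successively treated surgeries ('excellent' or 'good' overall efficacy rating"), and SAP 8.1 defines success for bleeding episodes and surgeries as "Excellent or good efficacy rating". Protocol version 03 defines success for bleeding episodes only (section 7.2.3), so the surgical success rule is the SAP's own.
- SAP 3.2 states: "No deviations from the protocol are planned".

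**The concern.** The same pair of component ratings leads to two different overall ratings, and the difference falls on the boundary that decides whether a surgery counts as a success. Protocol Table 3 reserves an intraoperative rating of None for surgeries in which hemostasis was not controlled and the factor replacement regimen had to be changed. Under the SAP table such a surgery becomes a success if the postoperative rating is Excellent. Under Table 5 of protocol version 03 it does not. The SAP text available for review gives no reason for the difference.

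What is at stake is the reported number of successfully treated surgeries. No hypothesis test, alpha level or power figure depends on it.

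**Working it through.** There is no planned figure to reproduce. The check compares the two tables cell by cell and then applies the SAP's success rule to each.

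**Inputs.** Protocol 7.2.5.3, Table 5; SAP 8.2; the success rule in SAP 8.1 and 5.9 (Excellent or Good).

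**Step 1, agreement.** The rows for intraoperative Excellent, Good and Moderate are identical. The row for intraoperative None is:

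| Postoperative rating | Protocol v03 | SAP 8.2 |
|---|---|---|
| Excellent | Moderate | **Good** |
| Good | Moderate | Moderate |
| Moderate | None | None |
| None | None | None |

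So 15 of 16 cells agree and 1 differs. Both tables have the same orientation, so the difference is not a transposition. Both rows are complete, so damage in text extraction is an unlikely cause.

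**Step 2, success cells by intraoperative row** (Excellent, Good, Moderate, None):

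- Protocol version 03: 3 + 2 + 1 + 0 = 6 of 16.
- SAP: 3 + 2 + 1 + 1 = 7 of 16.

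**Step 3, cells with at least one None component.** One row of 4 plus one column of 4, less the shared cell: 4 + 4 − 1 = 7. Successes among them: 0 of 7 in the protocol table, 1 of 7 in the SAP table.

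**Step 4, internal pattern.** There are 6 off-diagonal mirror pairs, in which the intraoperative and postoperative ratings are swapped. All 6 are equal in the protocol table; 5 of 6 are equal in the SAP table. The exception is the differing cell: None/Excellent is Good, but the SAP's own row for intraoperative Excellent, "Excellent Excellent Good Good Moderate", gives Moderate for Excellent/None.

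Scoring Excellent = 3, Good = 2, Moderate = 1, None = 0 shows the same thing. In the protocol table, all cells with the same score sum carry the same rating. In the SAP table this fails only at sum 3, where three cells are Moderate and None/Excellent is Good.

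**Step 5, effect on the result.** If *k* surgeries fall in this cell and are rated by the SAP table, the success count rises by *k* × 1 compared with the protocol table. If *k* = 0 the effect is zero. The documents plan no number of surgeries, so no percentage can be given. The cell counts in steps 2 and 3 describe the rules; they are not expected outcome rates, because the cells are not equally likely.

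**The case against.** The strongest objection is that the comparison uses a superseded protocol. SAP section 1 names a protocol dated 2017-09-07 with Amendment #04; the version available here is 03, dated 16-Jan-2017. Other SAP content also departs from version 03. The age subgroups split at 16 (SAP 4.6) rather than 17 (protocol 9.2.2), and the follow-up contact has a ±3 day window that version 03 lacks. Table 5 may have been amended too. In that case the SAP's statement that there are no deviations, which most naturally refers to the protocol it cites, would be true. The SAP's contents list also shows a protocol consistency check and a change-control page that are not in the text available for review, and a change may be recorded there. This stands as far as it goes: the documents show an inconsistency, not which table is right. It does not show that Table 5 was changed. SAP 2.5 still uses the under-17 limit for the PK group, so incomplete carry-over between versions is also possible.

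The second objection is that the Investigator assigns the overall rating, so the SAP table, headed a guide, may never be used to derive anything. SAP 5.9 and the flow chart support this, and on that reading the count follows the recorded rating. But SAP 8.2 also presents its table as the definition of the overall rating, so the SAP is not clear on the point.

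Third, nothing requires the table to be symmetric, since the two component ratings come from different raters using different criteria. That is right: the pattern in step 4 is consistent with a slip but does not prove one.

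Finally, the surgeon's and hematologist's ratings are presented separately, so an intraoperative None would stay visible in the report. This limits the harm but does not remove the discrepancy.

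**Conclusion.** The concern holds and is minor. SAP 8.2 and Table 5 of protocol version 03 differ in exactly one of 16 cells, and under the SAP's success rule that cell is a success in one table and a failure in the other. The effect on the success count is +1 for each surgery that falls in the cell and is rated by the SAP table, and zero otherwise. It is confined to the exploratory, descriptive surgery endpoint.

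That the two tables differ is certain. Whether the cause is a transcription error or an amendment is not known, because it depends on the 2017-09-07 protocol. The size of the effect assumes that the SAP table, and not only the Investigator's recorded rating, determines the overall rating.

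**What to change.** Compare SAP 8.2 with the overall-efficacy table in the protocol of 2017-09-07.

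- If that table gives Moderate for None/Excellent, correct the SAP cell.
- If an amendment changed the cell to Good, cite that amendment at SAP 8.2.
- In either case, add a sentence to SAP 5.9 stating that the success count uses the Investigator's recorded overall rating. This partly repeats what SAP 5.9 implies, but it removes the ambiguity created by SAP 8.2.

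The cost is one table check, at most one cell or one citation, and one sentence. The only downside is that the surgical success figure may be slightly less favourable.

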8.3 List of Tables, Listings, Figures

A complete lists of tables, listings figures (TLFs) will be given in a separate document which can be updated without updating the SAP. The list will serve as a reference for both the Sponsor, the trial statistician and the statistical programmer and includes the totality of statistical output to be produced. Therefore, this list will be approved by both parties before commencing the statistical programming.

All output will be headed with an appropriate heading specifying the study ID and abbreviated study title.

All output will be dated and have page numbers in the form 'Page [x / y]' where x denotes the current page within an output and y the total number of pages of that output.

All statistical output will identify the underlying analysis populations and indicate the number of subjects / events in this population (N) and the number of subject/events actually contributing to the particular output (n). All statistical output will be presented per treatment group and in total (if applicable).

All subject listings will contain additionally to the subject identification the analysis population and the treatment group.
